## 4.4 Subject Stopping Rules

Study drug dosing for an individual subject will be permanently discontinued for intolerable AEs that do not resolve to mild in severity (as defined in [Section 10.2.2.2](#)) or baseline within 48 hours of suspension of dosing and for study drug-related SAEs.

Administration of the study treatment will be discontinued if any of the following liver chemistry stopping criteria is met:

- Serum alanine aminotransferase (ALT) or aspartate aminotransferase (AST)  $\geq 3 \times$  ULN (upper limit of normal) and total bilirubin level  $\geq 2 \times$  ULN  
NOTE: Serum bilirubin fractionation should be performed if testing is available. If fractionation is unavailable, urinary bilirubin is to be measured via dipstick (a measurement of direct bilirubin, which would suggest liver injury).
- Serum ALT or AST  $\geq 5 \times$  ULN
- Serum ALT or AST  $\geq 3 \times$  ULN if associated with the appearance or worsening of rash or hepatitis symptoms (fatigue, nausea, vomiting, right upper quadrant pain or tenderness, fever, rash, or eosinophilia)

Any laboratory value that exceeds these limits should be repeated as soon as possible and, if confirmed, study treatment should be immediately discontinued. If a repeat laboratory assessment cannot be obtained within 3 days after receipt of the result showing the abnormal value, study drug should be discontinued.

A subject who meets the following ECG criteria will have study treatment discontinued:

- QTcF >500 msec or uncorrected QT >600 msec
- an increase in QTcF by  $\geq 60$  msec from Day 1 predose (baseline) with an absolute value of QTcF  $\geq 450$  msec (males) or  $\geq 470$  msec (females)

Treatment must be discontinued immediately in any subject who experiences a GTCS during the study if the subject had not had a GTCS prior to study entry. Subjects with worsening of seizures during the study should have treatment discontinued per investigator discretion. Unless consent for further follow-up is withdrawn, subjects who discontinue study drug for safety reasons should be followed in accordance with the schedule detailed in [Table 3](#).

Other reasons for treatment termination are provided in [Section 6.4](#).

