### **6.4.1 Follow-up Procedures for Subjects Who Withdraw/Discontinue Prematurely**

If a subject withdraws from the study, attempts should be made to contact the subject to determine the reason(s) for discontinuation. If a subject does not return to the clinic for follow-up visits, attempts should be made to contact the subject via phone, email, or mail. At least 3 documented attempts (one of which should be a certified letter) should be made to contact the subject before declaring a subject lost to follow-up. The Study Safety Representative must be informed as soon as possible if a subject discontinues or withdraws early.

The date and the reason for study drug discontinuation or subject withdrawal from the study must be recorded on the case report form (CRF). In case of early discontinuation or withdrawal of a subject, every effort must be made to report all study-mandated observations up to the time of discontinuation/withdrawal as completely as possible.

Subjects who are removed from treatment for AE(s) should be followed for resolution of the AE(s) (see [Section 10.2.3](#)) and should complete all assessments scheduled for the End-of-Study (EOS) Visit, as well as all assessments that they are capable of completing on the scheduled visit day if the decision to remove from treatment is made on a scheduled visit day. Likewise, if the investigator plans to temporarily interrupt dosing because of an AE and the decision is made on a scheduled visit day, the subject should complete all scheduled assessments that they are capable of completing on the visit day on which they appear.

If the reason for discontinuation/withdrawal is medical and the subject has not withdrawn consent, the subject should remain under the supervision of the investigator until the medical issue is resolved or otherwise declared stable.

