#### **10.2.3 Adverse Event Follow-up**

Adverse events requiring therapy must be treated with recognized standards of medical care to protect the health and well-being of the subject.

Any subject who has any AE (whether serious or non-serious) or clinically significant (in the investigator's opinion) abnormal laboratory test values will be evaluated by the investigator or qualified designee and will be treated and followed up until the symptoms or values return to normal or acceptable levels, as judged by the investigator and the sponsor.

All AEs, whether serious or non-serious, will be collected beginning at the time the ICF is signed through the telephone safety check on Day 33. All AEs should be followed until resolution or:

1. 30 days from onset; or
2. 30 days after the last dose of study drug; or
3. the subject is lost to follow-up (as defined in [Section 6.4.1](#)); or
4. the subject withdraws consent,

whichever occurs first.

SAEs will be reported up to 30 days after the last dose of study drug. A follow-up phone call will be made 30 days after the last dose of study drug for evaluation of any SAEs.

Any follow-up information available at the time of the subject's end of study will be included in the clinical study report.

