## Study PN004

Title (population)	A Phase IIa, Randomized, Multicenter, Double-Blind, Active Comparator- and Placebo-Controlled, Clinical Trial to Study the Safety and Efficacy of MK-8998 in Acutely Psychotic Patients with Schizophrenia (216 adult males (N=126) and females (N=90) 20-55 years old)	
Design	CX-8998 (8 mg BID) was compared with olanzapine and with placebo. N=86 randomized to CX-8998, including 49M/37F, 21-55 years old (mean age 37.4 years)	
Summary of findings	
Safety:
 

The most frequent TEAEs without regard to causality classified by MedDRA System Organ Class (SOC) in the CX-8998 group were Psychiatric Disorders (19/86 [22.1%] CX-8998 vs. 10/83 [12.0%] placebo); Nervous System Disorders (10/86 [11.66%] CX-8998 vs 6/83 [7.2%] placebo); and Gastrointestinal Disorders (9/86 [10.5%] CX-8998 vs 5/83 [6.0%] placebo). Among CX-8998 treated subjects, insomnia was the only TEAE that rose to a frequency of <math>\geq 5\%</math> (13/86 [15.1%] vs. 7/83 [8.4%] placebo).

No treatment-emergent SAE's occurred in CX-8998 treated subjects

 
TEAE's led to treatment discontinuation in 9/86 (10.5%) of CX-8998 treated subjects vs. 1/83 (1.2%) placebo treated subjects. Four of the CX-8998 discontinuations for AE were for worsening or exacerbation of schizophrenia, only one of which was assessed by the investigator as causally related to CX-8998.
	
Anti-Psychotic Efficacy:
 

Primary endpoint measure was mean change from baseline in the Positive and Negative Syndrome Scale (PANSS) total score at Week 4

CX-8998 was not statistically significantly different from placebo in the mean change from baseline in PANSS total score at Week 4 (Mean changes from baseline: CX-8998, -13.3; olanzapine -17.0; placebo -12.7)

For one of the secondary endpoints, responders were defined as those who demonstrated <math>\geq 20\%</math> improvement from baseline on the PANSS total score. CX-8998 was not statistically significantly different from placebo in the responder rate after 4 weeks of treatment (responder rates were: CX-8998, 57.4%; olanzapine, 66.7%; placebo, 48.3%)

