3.3.6. Presentations by Study Visit

When data are collected serially over time, individual data presentations may include by-visit or by-assessment displays. For these presentations, assessments will be presented according to the nominal assessment time as obtained from the eCRF. If the planned visit from the schedule of events is present, it will be used. If it is not present, then the closest assessment to the planned visit will be used. If two assessments have the same distance to the expected study assessment, the earlier value will be used.

All assessments will be presented in the listings.

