5.3.2. Safety Analysis

5.3.2.1. Vital Signs and ECGs

Descriptive statistics will be presented for actual values and for the change from baseline values for systolic and diastolic blood pressure, pulse rate, respiration rate, and weight by study visit. Blood pressure summaries will include recumbent and standing measurements, as well as the change from recumbent to standing (orthostatic changes).

Incidence of vital signs outliers will be presented by visit and time point, where applicable. Outliers for recumbent and standing vital sign parameters will be determined using the criterion in Table 1.

Descriptive statistics will be presented for actual values and for the change from baseline values for the ECG parameters of heart rate (bpm), PR interval (msec), QRS duration (msec), QT interval (msec), QTc interval (msec), and QTcF interval (msec) will be summarized by treatment group and study visit.

The incidence of ECG outliers will also be summarized by visit according to the following criteria:

- $QT > 500$ msec
- $QTcF > 450$ msec for males or $QTcF > 470$ msec for females
- $QTcF$ increases from baseline or pre-dose:
 - ≤ 30 msec
 - > 30 msec to ≤ 60 msec
 - > 60 msec

Table 1. Outliers for recumbent and standing vital sign parameters

Vital Sign	Criteria
Temperature	>38°C and $\geq 1^{\circ}\text{C}$ increase from baseline
Pulse	>120 bpm and >30 bpm increase from baseline <50 bpm and >20 bpm decrease from baseline ≥ 20 bpm increase from baseline ≥ 40 bpm increase from baseline ≥ 20 bpm decrease from baseline ≥ 40 bpm decrease from baseline
Systolic blood pressure	>180 mmHg and with >40 mmHg increase from baseline <90 mmHg and with >30 mmHg decrease from baseline ≥ 20 mmHg increase from baseline ≥ 40 mmHg increase from baseline ≥ 20 mmHg decrease from baseline ≥ 40 mmHg decrease from baseline
Diastolic blood pressure	>105 mmHg and with >30 mmHg increase from baseline <50 mmHg and with >20 mmHg decrease from baseline ≥ 10 mmHg increase from baseline ≥ 20 mmHg increase from baseline ≥ 10 mmHg decrease from baseline ≥ 20 mmHg decrease from baseline

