5.3.2.2. Clinical Laboratory Assessments

Actual values and changes from baseline in clinical laboratory assessments will be summarized by study visit.

Laboratory values outside the normal range for each parameter will be identified using shift tables. Each subject's hematology and blood chemistry values will be flagged as "low" (below the lower limit of normal/LLN), "normal" (within the normal range), or "high" (above the upper limit of normal/ULN) relative to the normal ranges of the central laboratory. Each subject's urinalysis values will be flagged as "normal" or "abnormal."

Shifts from baseline to high/normal/low status for hematology and blood chemistry parameters will be presented by study visit. Shifts from baseline to normal/abnormal status for urinalysis will be presented by study visit.

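### ECG, laboratory and vital-sign summaries go by nominal visit with no on-drug condition, so an early stopper's off-drug Day 26 value can be pooled with on-drug values and displace the on-drug value behind the stop

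*SAP*

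**What the plan says.** Changes from baseline in ECG, laboratory values and vital signs are among the primary safety endpoints (Protocol 3.3.1, SAP 5.3.1). The rules for summarising them are:

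- SAP 5.3.2.1: ECG parameters "will be summarized by treatment group and study visit". Vital signs and both outlier tables are also by visit. The reference to treatment group is a leftover in a single-arm study and has no bearing here.
- SAP 5.3.2.2: "Actual values and changes from baseline in clinical laboratory assessments will be summarized by study visit". The shift tables follow the same layout.
- SAP 3.3.6: "assessments will be presented according to the nominal assessment time as obtained from the eCRF". It adds: "If the planned visit from the schedule of events is present, it will be used". Failing that, the closest assessment is taken, with no limit on how far away it may be.
- SAP 4.2: everyone with at least one dose is in the safety population.

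For subjects who stop early, Protocol 4.4 says that, unless consent to follow-up is withdrawn, "subjects who discontinue study drug for safety reasons should be followed in accordance with the schedule detailed in" Table 3. Protocol 6.4.1 says that subjects removed for adverse events "should complete all assessments scheduled for the End-of-Study (EOS) Visit", and Table 2 footnote 1 is similar. Neither fixes the timing of those assessments relative to the last dose.

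SAP 1.1 states that nobody enrolled under amendments 4 or 5 and that the schedule and listed data follow amendment 3.

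**The concern.** A subject who stops for tolerability remains in the safety population. If that subject has a record carrying the Day 26 label, the SAP places it in the same row as values from subjects still on drug at the top of the titration. The row reads as an end-of-treatment result but mixes exposed and unexposed subjects.

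The outlier and shift tables raise the sharper issue. After Day 1, ECG and laboratory tests are scheduled only at Day 26 (Protocol Table 3; likewise the SAP 1.2 schedule). An earlier QTcF or liver value that met a stopping limit in Protocol 4.4 would therefore come from an unscheduled test. SAP 3.3.6 prefers the planned record, and there is no worst-post-baseline row. The outlier table could then show nothing for a subject who stopped because of an outlier. Any error from recovery runs towards no drug effect, in a small study whose primary objective is safety.

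**Working it through.** The plan gives no figure to reproduce: SAP 3.1 says that the sample size of up to 15 has no statistical basis. The check is of the text, followed by illustrations.

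**1. Is there an on-drug condition anywhere?** SAP 3.3.6, 4.2, 5.3.2.1 and 5.3.2.2 contain none. The nearest wording is the SAP 3.3.7 definition of a treatment-emergent laboratory abnormality, which refers to the treatment period. SAP 5.3.2.2 does not apply it to the visit summaries or shifts, and the treatment period is itself glossed as a span ending on Day 27.

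**2. Which record is used for an early stopper?** With a Day 26 record, that record is used. Without one, the closest assessment is used, whether on or off drug. How an exit assessment maps to a visit is not stated. Protocol Table 3 heads Day 26 as EOT and Day 33, a telephone contact, as EOS, while Protocol 7.2.8 calls Day 26 the End of Study Visit. The EOS assessments in 6.4.1 could therefore mean either.

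**3. Would a Day 26 value be off drug?** The fraction remaining is 0.5^(hours / half-life). Protocol Appendix D gives terminal half-lives of 9.7 to 13.2 h (PN001, young men) and up to 22.6 h (PN002, elderly men).

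| Last dose | Hours to Day 26 | 9.7 h | 13.2 h | 22.6 h |
|---|---|---|---|---|
| Day 20 | 144 | 0.003% | 0.05% | 1.2% |
| Day 24 | 48 | 3.2% | 8.0% | 23% |

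Unless the stop came in the last few days, plasma drug is essentially gone. This does not show when an ECG or laboratory value recovers. Protocol 10.2.3 requires subjects with abnormal values to be "treated and followed up until the symptoms or values return to normal or acceptable levels", which makes a recovered late value plausible but not certain.

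**4. Effect on the mean.** Let m be the mean change in subjects still on drug and let k of 15 be off drug with a change of zero. The pooled mean is ((15 − k)·m + k·0)/15 = m(1 − k/15). The shrinkage is 1/15 = 6.7%, 2/15 = 13.3% and 3/15 = 20% for k = 1, 2 and 3. An on-drug mean of 10 msec reads as 9.3, 8.7 or 8.0 msec.

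**5. Effect on an outlier cell (assumed values).** Take 14 subjects at +10 msec QTcF and one who stopped at +60 msec and returned to 0. The Day 26 mean is (14 × 10 + 0)/15 = 9.3 msec. Using that subject's on-drug value it is (14 × 10 + 60)/15 = 13.3 msec. The SAP category above 30 and up to 60 msec goes from 1 subject to 0. A rise of exactly 60 msec is not in the category above 60.

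**6. Chance of at least one early stop in 15,** 1 − (1 − p)^15, at assumed rates p:

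- p = 5%: 0.75 expected; 1 − 0.95^15 = 0.537 (54%).
- p = 20%: 3.0 expected; 1 − 0.80^15 = 0.9648 (96%).

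The one earlier rate in the protocol falls inside this range. In PN004, at 8 mg BID, "TEAE's led to treatment discontinuation in 9/86 (10.5%) of CX-8998 treated subjects": 15 × 9/86 = 1.57 expected and 1 − (77/86)^15 = 81%. Those were acutely psychotic patients with schizophrenia, and 4 of the 9 stops were for worsening or exacerbation of schizophrenia. Without these, 5/86 = 5.8% gives 0.9 expected and 59%.

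**The case against.** The strongest reply has four parts.

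- **Protocol version.** The follow-up rule in Protocol 4.4 belongs to a version under which no one enrolled. The amendment 3 stopping text is not among the documents. A reader might infer that the analysed early stoppers were kept on the Table 3 schedule to Day 26; that cannot be shown. This stands. The gap in SAP 3.3.6, 5.3.2.1 and 5.3.2.2 does not depend on it.
- **Timing.** An exit assessment done promptly at removal would be close to the last dose and not recovered. This also stands: pooling of recovered values is a possible result of the rules, not a stated one. Nothing in the SAP distinguishes the two cases.
- **Other visits.** The SAP 1.2 schedule also appears to place vital signs at the home visits on Days 8 and 20, so Day 26 is not the only later time point for them. For ECG and laboratory tests it is.
- **Visibility elsewhere.** Non-completion due to TEAEs is itself an endpoint. TEAEs leading to discontinuation and TEAEs by dose are tabulated, and all assessments are listed. A reader might infer that a safety signal would vanish from the report; it would not. What can be lost is its place in the quantitative ECG, laboratory and vital-sign tables.

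The study is also descriptive, with no decision threshold on these means. That limits the consequence but does not make a mixed row easier to interpret.

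**Conclusion.** The point holds as a gap in the SAP. Its visit rules allow an off-drug value to stand as the Day 26 result, and they let that value displace an on-drug value that led to the stop from the outlier and shift tables. The effect is conditional on three things: at least one early stop, a later assessment labelled or mapped as Day 26, and recovery by then. A persistent abnormality would still show.

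Given those conditions, the mean change falls by 6.7% per such subject if all 15 contribute, and one outlier count can go from 1 to 0. The 54% to 96% chance concerns only the first condition and rests on assumed rates. The PN004 rate should not be read as a forecast for this population. The documents do not support saying that such pooling did occur, or that the adverse-event analysis is affected.

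**What to change.** Before database lock:

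1. In SAP 5.3.2.1 and 5.3.2.2, add to the outlier and shift tables a row for the worst on-treatment post-baseline value, including unscheduled assessments.
2. Flag each assessment as on or off drug from the recorded date of last dose, for example on drug if no later than one calendar day after it. Limit the Day 26/EOT row to on-drug values and show later values in a separate off-drug row. A date rule is preferable to an hour rule: SAP 3.3.7 already draws the last-dose date from the End of Study form or the AiCure transfer, whereas the documents mention recording the last-dose time only with PK draws.
3. If a row for change at the last on-treatment value is added, show it by dose at assessment or leave out the Day 1 post-dose reading. Otherwise readings after a single 2 mg dose are averaged with readings at 20 mg/day, which may also dilute the result.
4. State how early-termination assessments map to visits. Protocol 4.4 must be reconciled with Table 2 footnote 1 and 6.4.1, and the EOT and EOS labels in Table 3 with 7.2.8. The amendment 3 equivalents should be checked, since they govern the analysed subjects.

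The cost is SAP wording, two or three extra table rows, and a Day 26 row whose n falls by the number of early stoppers. No new data collection appears to be needed.

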## 4.6 Dose Adjustments / Toxicity Management

Adverse events will be graded for intensity by the investigator (see [Section 10.2.2.2](#)).

Dosing will be discontinued for all study drug-related SAEs.

A member of the study staff will contact any subject who is suspected of experiencing neuropsychiatric AEs to determine the need for an unscheduled visit before further dose escalation may proceed. Subjects who are experiencing any AEs may also be asked to return for an unscheduled visit. Subjects who are suspected of experiencing a neuropsychiatric event should be seen in person.

In all subjects with intolerable AEs (as defined in [Section 10.2.1](#)) that are considered related to study drug, treatment should be suspended for up to 48 hours or until the AE resolves to a tolerable level of severity, whichever is earlier. In subjects who are unable to tolerate 6 mg BID, 8 mg BID or 10 mg BID, dosing may then be resumed at a previously tolerated lower dose. Only a single dose-step reduction (i.e., 10 mg BID to 8 mg BID, 8 mg BID to 6 mg BID, or 6 mg BID to 4 mg BID) is permitted. Reescalation of the dose is NOT permitted. Dosing should be discontinued if there is recurrence of intolerable AEs after the dose reduction. Subjects who experience intolerable AEs while receiving the 2 mg BID or 4 mg BID dose will be discontinued from treatment. Table 2 details dose reductions by dose level.

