3.3.7. Definitions and Terminology

Age

The age of a subject is defined as the number of whole years between the subject's birth date and the date of informed consent.

Day 1 (Baseline)

Day 1 is the earliest day that study drug is initiated.

Study Day

Study Day is defined relative to Day 1 as follows: Study Day = Date of event – Date of Day 1 +1*(1 if date of event \geq Date of Day 1, 0 otherwise).

Study Visit

Study Visit is the nominal visit as recorded on the eCRF.

Baseline Value

For purposes of analysis, the baseline value is defined as the last non-missing value obtained prior to initiation of study drug.

Change from Baseline

Change from baseline for a given endpoint is defined as the Study Day X value minus the baseline value.

Percent Change from Baseline

Percent change from baseline for a given endpoint is defined as the Study Day X value minus the baseline value, quantity divided by the baseline value, multiplied by 100.

$$\text{Percent Change from Baseline} = (\text{Study Day X} - \text{Baseline})/\text{Baseline} * 100$$

Days on Study

Days on study is defined as the number of days from the date of study drug initiation to the final study visit (includes in home or in clinic assessments).

Completer

A subject is defined as a completer if he/she completes the Day 26 EEG and Day 27 dosing regardless of completing the Day 33 visit.

Treatment Period

The treatment period is the period during which a subject receives study drug (i.e., first dose through Day 27).

Days on Study Drug

Days on study drug is defined as the number of days in the treatment period. The date of the last dose of study drug as recorded on the End of Study Visit form or from the AICure electronic data transfer.

Total Study Drug Expected (capsules)

The total study drug expected is defined as the total number of capsules expected to be taken as recorded from all sources and reported from the AICure system.

Total Study Drug Received (capsules)

The total study drug received is defined as the total number capsules of taken as recorded from all sources and reported from the AICure system.

Total Study Drug Received (mg)

The total study drug received (mg) amount will be multiplied by 2 for subjects receiving CX-8998 to calculate the amount of study drug received in mg (i.e., each capsule is 2 mg).

Treatment Compliance

Treatment compliance will be calculated for each subject as a percentage using the following formula:

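### By-visit ECG, vital-sign and laboratory abnormality tables can miss a transient on-treatment abnormality, because no any-post-baseline summary is planned

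*SAP*

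**What the plan says.** Changes from baseline in ECG, laboratory values and vital signs are among the primary safety endpoints (protocol 3.3.1, SAP 5.3.1). The SAP tabulates abnormal values visit by visit:

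- ECG (SAP 5.3.2.1): "The incidence of ECG outliers will also be summarized by visit according to the following criteria".
- Vital signs (SAP 5.3.2.1): outlier incidence is by visit and, where it applies, time point.
- Laboratory (SAP 5.3.2.2): "Shifts from baseline to high/normal/low status for hematology and blood chemistry parameters will be presented by study visit".

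SAP 3.3.7 defines the visit: "Study Visit is the nominal visit as recorded on the eCRF". SAP 3.3.6 then decides which record fills a visit. First, "If the planned visit from the schedule of events is present, it will be used". Failing that, "If it is not present, then the closest assessment to the planned visit will be used", with ties going to the earlier value. Finally, "All assessments will be presented in the listings".

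The table list in SAP section 10 has one laboratory shift table (14.3.4.5), one ECG outlier table (14.3.5.1.2) and one vital-sign outlier table (14.3.5.2.3). Neither the text nor the titles provide for a worst-value or any-time row.

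The protocol expects extra measurements. Section 4.6 says "Subjects who are experiencing any AEs may also be asked to return for an unscheduled visit", and note 3 to the SAP's own schedule also allows for such visits. Section 4.4 says of the liver limits: "Any laboratory value that exceeds these limits should be repeated as soon as possible". Section 10.1.7 allows abnormal ECGs to be repeated, and section 10.1.3 calls for blood pressure and pulse whenever a subject seems faint or dizzy.

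**The concern.** Extra measurements in this trial arise mainly because something looks wrong. A table that takes one planned value per visit passes over them when the planned value exists. The values passed over are more likely than average to be abnormal. If the finding has resolved by Day 26, the subject is counted as normal on a primary safety endpoint.

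A second gap lies beside it. Protocol 11.5.2 commits to two laboratory summaries: how many subjects (and what percentage) had a treatment-emergent abnormality, and the shifts from baseline. SAP 3.3.7 defines such abnormalities over the whole treatment period, but section 10 lists only the shift table, and section 7 does not name the first summary among the analyses dropped.

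Scale is also lost. A low/normal/high flag puts ALT at 1.1 times and at 6 times the upper limit of normal (ULN) in the same cell, although the liver criteria in protocol 4.4 are written in multiples of ULN.

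**Working it through.** The plan gives no figure to reproduce. The check is of the selection rule, the schedule and the resulting gap.

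**1. What the rule does in each situation.** The days in these cases are illustrations.

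| Situation | Record used for Day 26 | Result in the by-visit table |
|---|---|---|
| High unscheduled value on Day 15, normal planned value on Day 26 | Planned Day 26 | Normal; Day 15 value in listings |
| High value on Day 15, normal follow-up on Day 20, no planned Day 26 value | Closest: 26 − 20 = 6 days, against 26 − 15 = 11 days | Normal; the recovered value is chosen |
| High value on Day 15, nothing later | Day 15, as the closest | High |
| High planned value on Day 26, normal repeat afterwards | Planned Day 26 | High; the repeat does not replace it |

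The first two rows are the defect. The second is realistic because protocol 10.2.3 has clinically significant abnormal values followed until they are normal or acceptable.

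**2. When laboratory tests and ECGs are planned.** The SAP schedule (1.2, amendment 3) and protocol Table 3 agree: Screening, Day 1 and Day 26. The Day 26 window is ±1 day. Vital signs differ: the SAP schedule marks them at intermediate visits too.

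**3. Length of the gap for laboratory tests and ECGs.** Days 2 to 25 are 25 − 2 + 1 = 24 days.

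- SAP treatment period, Days 1 to 27 (3.3.7): 24/27 = 89%.
- Current protocol, Days 1 to 26 (10.2.1): 24/26 = 92%.

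The only planned exception is a Day 26 visit held on Day 25. Three of the five dose steps (8, 12 and 16 mg/day, Days 3 to 20) contain no planned laboratory test or ECG.

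**4. Weight of one subject.** The SAP enrols at most 15 (3.1). One subject is 1/15 = 6.7 percentage points, and more if fewer contribute data.

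**5. Promised against planned.** Protocol 11.5.2 has an incidence summary and shifts. SAP 5.3.2.2 and Table 14.3.4.5 have shifts only. SAP section 7 is silent on the difference.

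**The case against.** A reader might infer that the tables use planned visits only, and that nothing measured on Days 2 to 25 can ever reach a table. The documents do not support that:

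- The 3.3.6 fallback can admit an unscheduled value when the planned one is missing.
- A pre-dose repeat can become the baseline value (SAP 3.3.7).
- Day 26 may fall on Day 25, and subjects removed from treatment for adverse events complete the end-of-study assessments (protocol 6.4.1), possibly on Days 2 to 25.
- Protocol 10.2.1 treats clinically significant laboratory abnormalities as adverse events, so they can reach the adverse event tables. SAP 3.3.7 is weaker, saying only that they may be recorded that way.
- The SAP does not expressly rule out a row for unscheduled visits. The omission is inferred from 3.3.6.

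A reader might also infer that repeats hide abnormal results. For a repeat of an abnormal planned value the rule works the other way, since the planned value stays. Protocol 10.1.7 notes that ECG repeats may serve to exclude poor lead placement, so a crude worst-value row could count artefacts.

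Other points stand in part. Unscheduled visits need not include a laboratory test or ECG, and a new row cannot supply measurements that were never taken. SAP 1.1 says no one enrolled under amendments 4 and 5. The repeat rules cited come from the current protocol, and the amendment 3 text is not available; only the unscheduled visits are confirmed by the SAP's own schedule. By-visit summaries include a maximum, so a very high planned ALT would be visible there. Finally, this is a single-arm descriptive study, and listings for at most 15 subjects can be read in full.

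These points limit the concern but do not remove it. The fallback selects by closeness, the adverse event route depends on reporting, and none of them supplies the missing incidence summary.

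**Conclusion.** The concern holds in limited form. When the planned assessment exists, unscheduled and repeat values stay out of the by-visit outlier and shift tables, and no any-post-baseline summary captures them. When it is missing, the closest value is taken, whatever its severity. A transient laboratory or ECG abnormality between Day 1 and Day 26 can thus be tabulated as normal unless it is also reported as an adverse event. The laboratory incidence summary promised in the protocol is missing without explanation.

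The size is a window of 24 of 27 treatment days (24 of 26 in the current protocol) and at least 6.7 percentage points per missed subject. Neither figure shows that any value was missed; that number is unknown.

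The conclusion assumes that 3.3.6 governs these three tables, that no unscheduled row is added in programming, and that amendment 3 provided for repeats much as the current protocol does. The listings keep every value and no formal hypothesis is tested (protocol 11.2), so this is a cheap improvement and not a must-fix.

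**What to change.** In Tables 14.3.4.5, 14.3.5.1.2 and 14.3.5.2.3, add a row for *any on-treatment post-baseline value*. It should give the worst value per subject and include unscheduled, repeat and early-termination assessments. Where a parameter can be abnormal in both directions, take the worst separately for high and low. Keep the by-visit rows.

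For ECGs, exclude tracings that the reviewing physician rejects as technically invalid, and footnote how many were excluded.

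Use the laboratory row to supply the count and percentage promised in protocol 11.5.2. Before programming it, settle the SAP 3.3.7 definition: as worded, it counts only abnormalities in subjects whose baseline was already outside the normal range. Show worst ALT, AST and bilirubin in the multiples of ULN already used in protocol 4.4.

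The cost is a few lines of SAP text, one derived record per parameter (two where both directions matter) and a little more programming. Reported abnormality rates may be slightly higher.
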